- 11. Subjects with any known hypersensitivity to Kybella (deoxycholic acid) or any of the inactive ingredients: benzyl alcohol, dibasic sodium phosphate, sodium chloride, sodium hydroxide, hydrochloric acid
 - B. Source of subjects and recruitment methods
 Subjects will be recruited by flyers and handouts placed in the UCSD Dermatology
 clinic. Eligible patients will be determined from the inclusion and exclusion criteria.
 Eligible patients will be informed of the proposed study and its purpose and given the
 opportunity to ask any questions.

Standard HIPAA authorization to collect research data from the subject's medical record will be obtained at the time of informed consent.

C. Equitable Selection of Subjects

The risks and benefits of the research are fairly distributed among the populations that stand to benefit from it. Although the risk of this study is minimal, to be prudent, pregnant women will be excluded because of the potential harm posed to the fetus.

IV. Subject Enrollment

A. Number of subjects

15 subjects will be enrolled in the study.

B. Methods of enrollment

Subjects interested in participating in the study may contact one of the investigators. The study objectives, inclusion and exclusion criteria, possible risks and benefits of the study, and the information included in the informed consent form shall be discussed with prospective study participants. Subjects who believe they meet the exclusion and inclusion criteria and remain interested in the study shall be invited to come in for their screening visit. During the screening visit, the investigator will interview the subject and perform a simple clinical examination, particularly examining the thighs. Following the investigator's determination that the inclusion and exclusion criteria are met, the subject be invited to participate in the study.

C. Procedures for obtaining informed consent

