There will be no randomization. Study participants will be treated with deoxycholic acid (Kybella) 10 mg/ mL injected subcutaneously, targeting the medial thigh deep fat compartment (pre-fascial). Subjects will receive deoxycholic acid 2 mg/ cm², with injections of 0.2 mL spaced evenly 1 cm apart within the treatment area. Bilateral upper inner thighs will be treated. Each treatment will consist of a maximum of 8 mL (40 injection sites) of the study drug, with a maximum of 4 mL (20 injection sites) of the study drug for each thigh. All treatments will be performed by a study physician. Subjects will receive 1 to 4 treatment sessions, each spaced 6 weeks +/- 1 week. Treatment #2, #3, or #4 will be pursued if patient desires more treatment, and if there is sufficient fat for treatment, per investigator's judgment.

V. Study Procedures

a) Study visits and parameters to be measured
 All visits in this study will be performed at the UCSD Dermatology Clinic, 3rd floor,
 [name].

Screening/Baseline Visit (Visit 1, Day -14 to 1)

This visit is expected to take approximately 1 hour. The following describes the procedures performed at this visit.

Prior to any screening assessments, informed consent will be obtained by the
investigator. When the subject fully understands the nature of the study and its risks,
the subject will be asked to sign and date the informed consent form. The
investigator will then sign and date the form.

- 2. A detailed medical history of information pertaining to treatment will be obtained.
- 3. The investigator will perform a relevant physical examination.
- 4. Patient's weight will be obtained.
- 5. The subject will be asked to complete the Subject Self-Rating Scale (0 to 6 scale).
- 6. If the subject meets the criteria for the study, the subject will be assigned the next consecutive subject number.
- 7. Females of childbearing age will undergo a urine pregnancy test
- 8. The investigator will determine the patient's eligibility for the study.

First treatment (Visit 2, Day 1)

The treatment visit is expected to take approximately 1 hour. The first treatment may be combined with Screening/ Baseline.

Prior to Kybella treatment:

- 1. Patient will be asked to complete the Subject Self-Rating Scale, rated from 0 to 6.
- 2. Patient's weight will be obtained.
- 3. Concomitant medications and procedures will be confirmed and recorded.
- 4. The investigator will perform a relevant physical examination.

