 Vertical distance of this site from the floor will be measured, such that thigh circumference measurements at all following study assessments are performed at the same site.

- 7. Caliper measurement of inner thigh skin-fold thickness will be obtained.
- Caliper measurement will be performed at site of maximum bulge at Screening.
 Vertical distance of this site from the floor will be measured, such that caliper measurements at all following study assessments are performed at the same site.
- 8. Thigh gap measurement will be obtained.
- Patient will be asked to stand with legs at a fixed distance apart. Measurement
 will be performed between sites of maximum bulge at Screening. Vertical
 distance of these sites from the floor will be measured, such that thigh gap
 measurements at all following study assessments are performed at the same sites.
- 9. Pre-treatment photographs will be taken.
- Patients will be asked to stand with feet apart at a uniform distance.
 Anteroposterior and posteroanterior photos will be taken.

Treatment:

10. Deoxycholic acid (Kybella) 10 mg/ mL will be injected subcutaneously, targeting the medial thigh deep fat compartment (pre-fascial). Subjects will receive deoxycholic acid 2 mg/ cm2, with injections of 0.2 mL spaced evenly 1 cm apart within the treatment area. Bilateral thighs will be treated. Each treatment will consist of a maximum of 8 mL (40 injection sites) of the study drug, with a maximum of 4 mL (20 injection sites) of the study drug for each thigh. All treatments will be performed by a study physician.

Post-Treatment Phone Call #4 (~Day 108 to 150)

Phone call expected to take 5-10 minutes.

1. Two days after treatment, patient will be called and asked to report adverse events since last treatment. All adverse events will be recorded.

Week 4 Follow Up (~Day 134 to 176)

Visit expected to take 1 hour. The visit will take place 4 weeks after the last treatment.

- 1. Patient will be asked to complete Subject Self-Rating Scale, rated from 0 to 6.
- 2. Patient will be asked to complete Post-Treatment Satisfaction Questionnaire.
- 3. Concomitant meds and procedures will be confirmed and recorded.
- 4. Adverse events will be confirmed and recorded.
- 5. Patient weight will be obtained.
- 6. A relevant physical exam will be performed by the investigator.
- 7. Thigh circumference measurement will be obtained with anthropometric tape measure.
 - Thigh circumference will be measured at site of maximum bulge at Screening.

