 distance of these sites from the floor will be measured, such that thigh gap
 measurements at all following study assessments are performed at the same sites.
- 10. Follow-up photographs will be taken.
 - Patients will be asked to stand with feet apart at a uniform distance.
 Anteroposterior and posteroanterior photos will be taken.

b) Drugs to be used

Deoxycholic acid (Kybella) 10 mg/ mL will be injected subcutaneously, targeting the medial thigh deep fat compartment (pre-fascial).

c) Data to be collected and when data is to be collected

Data to be collected throughout the study includes the items listed in Schedule of Events.

VI. Biostatistical Analysis

A. Study endpoints

1. Primary Endpoint:

The primary endpoint will be safety endpoint, as defined by the incidence rate of patients who experience:

- a) Any adverse event (AE) ascertained by patient report or physician evaluation
- b) One or more serious adverse events (SAE) as defined by CTCAEv4
- c) Adverse events leading to study drug discontinuation.

2. Secondary Endpoints:

- a) Efficacy, defined as reduction in inner thigh fat, measured as follows:
 - i. Change in thigh circumference, as recorded with anthropometric tape measure.
 - Thigh circumference will be measured at site of maximum bulge at Screening. Vertical distance of this site from the floor will be measured, such that thigh circumference measurements at all following study assessments are performed at the same site.
 - ii. Change in inner thigh skin-fold thickness, as measured by calipers
 - Caliper measurement will be performed at site of maximum bulge at Screening. Vertical distance of this site from the floor will be measured, such that caliper measurements at all following study assessments are performed at the same site.
 - iii. Increase in "thigh gap," measured with patient standing with legs at a fixed distance apart. Measurement will be performed between sites of maximum bulge at Screening. Vertical distance of these sites from the floor will be measured, such that thigh gap

measurements at all following study assessments are performed at the same sites.

- iv. Percent accuracy by three blinded physicians in correctly identifying baseline photographs, upon independent review of before-and-after clinical photographs of the treatment area.
- Patients will be asked to stand with feet apart at a uniform distance.

 Anteroposterior and posteroanterior photos will be taken.

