- b) Patient satisfaction related to study treatment:
 - i. Improvement in patient satisfaction, as measured by
 Subject Self-Rating Scale, a 0 (extremely dissatisfied) to 6
 (extremely satisfied) scale
 - ii. Scores on additional post-treatment patient satisfaction questionnaire

B. Statistical methods

This is a small descriptive study, with the primary safety endpoint of the incidence rate of patients who experience:

- 1) Any adverse event (AE) ascertained by patient report, physician evaluation, or laboratory value
- 2) One or more serious adverse events (SAE) as defined by CTCAEv4
- 3) Adverse events leading to study drug discontinuation.

The safety analysis will be based on the safety population, which is defined as all patients who have received at least one dose of study medication and who have had at least one post-baseline safety evaluation.

Adverse events will be explored for trends.

The efficacy analysis will be based on the intent-to-treat (ITT) population. In the ITT population, patients will be counted in the treatment group upon informed consent and completion of Baseline measurements, regardless of receiving any dose of study medication.

In the case of a subject's early termination from study, missing values will be imputed using last observation carried forward (LOCF) method.

Baseline values will be those values measured on day of screening, which may be combined with Day 1.

Reduction in inner thigh fat, as measured by tape measure and calipers, will be presented as change in millimeters or centimeters, and presented descriptively. Percent accuracy by three independent blinded physicians in correctly identifying baseline photographs, when comparing before-and-after clinical photographs of the treatment area, will be reported. Patient satisfaction scores on Subject Self-Rating scale and post-treatment patient satisfaction questionnaire will be presented descriptively.

VII. Risks and Discomforts

A. Complications of treatment procedure/drug side effects and toxicities

Deoxycholic acid will be injected subcutaneously in the treatment area by the principal investigator [name], or by a member of the study team who is a UCSD Dermatology resident physician, under direction of [name].

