Common side effects of deoxycholic acid injection are injection site reactions, including swelling, pain, numbness, redness, and hardness of treatment area. Bruising, itching, warmth, hardness, tingling or burning sensation, skin tightness, hair loss, open sores (ulcers), damage, and tissue cell-death (necrosis) around the injection site are other possible side effects.

Deoxycholic acid injection in submental fat has been rarely associated with nerve injury, headache, mouth or throat pain, hypertension, nausea, or difficulty swallowing.

Patients will be asked regarding allergy to medications. Allergic reaction may occur with any medication.

Subjects will be provided post-treatment instructions (see attached).

B. Psychosocial (non-medical) risks

We do not anticipate any psychosocial risks due to this study. However, if any participants experience emotional distress during the study we will assist them to resolve this stress with appropriate referrals. Steps to prevent this outcome will include detailed explanation of the study and what to expect from the study treatment.

VIII. Potential Benefits

A. Potential benefits to participating individuals

Subjects participating in the study may receive the benefit of reduced inner thigh fat due to the study treatment.

B. Potential benefits to society

The results of this study will help us acquire information that may lead to the development of a new treatment for reduction of inner thigh fat.

IX. Cost and Remuneration

a. Remuneration

Subjects will receive financial compensation for their participation in the study.

Screening and treatment visits will not be compensated. Subjects will receive \$50 per inperson follow-up visit. Therefore, subjects will receive a total of \$100 for completing the entire study.

b. Cost

There will be no cost to the patient to participate in this study.

X. Monitoring and Quality Assurance

A. Independent monitoring of source data

At this time, we do not anticipate a need for an independent monitor as our monitoring of the data will be sufficient to ensure the validity and integrity of the data and adherence to the IRB-approved protocol.

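### The blinded photograph endpoint is not specific to fat reduction: a correct pick prompted by a visible treatment mark counts as efficacy

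*Combined protocol and SAP*

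**What the plan says.** Section VI.A.2.a opens with "Efficacy, defined as reduction in inner thigh fat, measured as follows" and lists four measures: thigh circumference, skin-fold thickness, thigh gap and, as item iv, "Percent accuracy by three blinded physicians in correctly identifying baseline photographs". The material is read "upon independent review of before-and-after clinical photographs of the treatment area". Section VI.B repeats the endpoint and says only that the percentage, "when comparing before-and-after clinical photographs of the treatment area, will be reported". It gives no guessing level, interval or threshold.

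Neither section gives the question put to the readers, tells them to judge fat or contour, or says which follow-up image is the after photograph. Photograph control is limited to stance and two views. Section V.a schedules photographs before each treatment and at the Week 4 and Week 12 follow-ups. For Week 4, "The visit will take place 4 weeks after the last treatment".

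Section VII.A names swelling and redness among the common injection-site reactions. It mentions bruising and skin tightness as well, and adds that "hair loss, open sores (ulcers), damage, and tissue cell-death (necrosis) around the injection site are other possible side effects".

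On size and design, section IV.A states that "15 subjects will be enrolled in the study" and section IV.D that "There will be no randomization". There is a single treated arm.

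**The concern.** What is defined differs from what is scored. The definition concerns fat; the score concerns time order. A reader who notices thinned hair, a healing ulcer or discoloured skin can name the earlier photograph correctly even if the thigh has not changed in size. That answer is then counted under efficacy, although the same lesion would count as an adverse event in the primary endpoint.

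This matters because item iv is the only efficacy measure described as blinded. The study is open-label, and section X.B has the investigators make the efficacy assessments. With no untreated or sham pairs, nothing in the design shows how much of the accuracy comes from cues other than fat. An accuracy figure reported alone could be read as blinded confirmation of fat loss when it shows only that the photographs were distinguishable.

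**Working it through.** The plan gives no target, chance level or sample-size reasoning for item iv, so there is no figure of its own to reproduce. The calculation below is an illustration.

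**Inputs from the documents.** 15 subjects (section IV.A) and three readers (section VI.A.2.a.iv).

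**Assumptions.** One pair per subject, so 15 × 3 = 45 readings. No change in fat. A share q of pairs carries a mark that all three readers notice and read correctly. All other readings are independent guesses at 50%.

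**Step 1: expected accuracy.**

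Accuracy = q × 1 + (1 − q) × 0.5 = 0.5 + q/2.

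**Step 2: chance of an impressive figure.** The number of marked pairs K is binomial (15, q). Marked pairs give 3K correct answers, and the other 45 − 3K readings are binomial with probability 0.5. Summing over K gives:

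| q (assumed) | Expected accuracy | Chance of at least 30/45 (67%) | Chance of at least 36/45 (80%) |
|---|---|---|---|
| 0 | 50% | 1.8% | below 0.01% |
| 10% | 55% | 9.5% | 0.1% |
| 20% | 60% | 26% | 1% |
| 40% | 70% | 70% | 15% |
| 60% | 80% | 96% | 58% |

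An expected accuracy of 80% from marks alone requires 0.5 + q/2 = 0.8, so q = 60%.

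**Step 3: cues that mislead.** Suppose a further share s of pairs shows swelling and every reader takes the larger thigh for baseline. Then accuracy = q + (1 − q − s) × 0.5 = 0.5 + (q − s)/2. The net shift is downward whenever s exceeds q.

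**Step 4: what the documents say about q.** They give no frequency of visible marks at either follow-up. The only durations for visible local effects are in section I.B and come from a phosphatidylcholine series, a different product: 48 to 72 hours for bruising, edema and erythema, and at most 30 days for nodules. The Week 4 photograph falls at 4 × 7 = 28 days after the last treatment, just inside the nodule limit; the Week 12 photograph, at 84 days, is well outside it. Treatments are 6 weeks apart, plus or minus 1, and photographs at those visits precede injection. They are therefore at least 5 weeks after the previous session, and Week 4 is the earliest post-treatment image.

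**Step 5: effect of the change.** If a share r of marked pairs can still be recognised after cropping, accuracy with no fat change is 0.5 + qr/2. With r = 0 it is 50%. With r = 0.5 it is 55%, 60% and 65% at q = 20%, 40% and 60%, against 60%, 70% and 80% under the present task. These figures assume that no reader answers that there is no difference. If a share d of guessed readings is so answered and scored as not correct, guessing yields (1 − d)/2, so 50% is then an upper limit for guessing.

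**The case against.** A reader might infer that item iv measures treatment marks instead of fat, or that it is biased upward. The documents support neither.

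- Visible fat loss also raises accuracy, so the endpoint does respond to what it is meant to measure. The defect is lack of specificity.
- Upward bias needs marks still visible at least four weeks after the last treatment. Section VII.A lists possible effects without rates or durations, and the durations in section I.B suggest that most marks are brief, though for another product. That section also lists ecchymosis and induration including fibrosis as common with deoxycholic acid, but gives no duration for them.
- Swelling, among the common reactions in section VII.A, could push accuracy down.
- High accuracy from marks alone needs a large q. Nothing in the documents supports 60%.

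The consequence is also limited. The study is descriptive, its primary endpoint is safety, no test or success criterion rests on item iv, and circumference, calipers and thigh gap address size directly. Physical examination and adverse-event recording take place at the same follow-up visits as the photographs, so accuracy could be checked against them.

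All of this stands, and it limits the point to how item iv is interpreted. It does not answer the central difficulty: the three direct measures are not described as blinded, and nothing in the scoring of the blinded one separates fat loss from any other visible change.

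**Conclusion.** Item iv is not specific to fat reduction. Its accuracy can be distorted by visible local effects, and may exceed 50% with no change in fat: 55%, 60% and 70% if 10%, 20% and 40% of pairs carry a mark that all readers use. Those shares are assumptions, as are one pair per subject and independent guessing elsewhere. The size and even the direction of any net distortion are unknown from the documents. The primary safety endpoint and the three direct size measures are unaffected. This is a cheap improvement to a secondary descriptive endpoint and does not invalidate the study.

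**What to change.** Settle the following before any image is read:

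1. Put this question to the three blinded readers: *Which photograph shows less inner thigh fat, or is there no difference?* Score an answer of no difference as not correct.
2. Use the Week 12 photograph as the after image. Crop both images to the thigh contour so that skin marks are hidden, and randomise the display order. Rewording alone is not enough, since a reader who sees an ulcer still knows which image came later. Greyscale would not hide ulcers or hair loss. Cropping cannot remove swelling, which alters the contour; the Week 12 image is the scheduled one furthest from treatment.
3. Report the percentage against the 50% guessing level.
4. Identify pairs with visible marks from the physical examination and adverse-event record of the same visit, or by flagging only after all readings are locked. Flagging during the reading would draw attention to the marks. Report the result with and without those pairs.

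The cost is new wording on the reader form and simple image preparation, with no extra readers, visits or subjects. The downside is a slightly less favourable figure, because answers of no difference count against accuracy.

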 Vertical distance of this site from the floor will be measured, such that thigh circumference measurements at all following study assessments are performed at the same site.
- 8. Caliper measurement of inner thigh skin-fold thickness will be obtained.
 - Caliper measurement will be performed at site of maximum bulge at Screening.
 Vertical distance of this site from the floor will be measured, such that caliper measurements at all following study assessments are performed at the same site.
- 9. Thigh gap measurement will be obtained.
 - Patient will be asked to stand with legs at a fixed distance apart. Measurement
 will be performed between sites of maximum bulge at Screening. Vertical
 distance of these sites from the floor will be measured, such that thigh gap
 measurements at all following study assessments are performed at the same sites.
- 10. Follow-up photographs will be taken.
 - Patients will be asked to stand with feet apart at a uniform distance.
 Anteroposterior and posteroanterior photos will be taken.

Week 12 Follow Up (~Day 190 to 232)

Visit expected to take 1 hour. The visit will take place 12 weeks after the last treatment.

- 1. Patient will be asked to complete Subject Self-Rating Scale, rated from 0 to 6.
- 2. Patient will be asked to complete Post-Treatment Satisfaction Questionnaire.
- 3. Concomitant meds and procedures will be confirmed and recorded.
- 4. Adverse events will be confirmed and recorded.
- 5. Patient weight will be obtained.
- 6. A relevant physical exam will be performed by the investigator.
- 7. Thigh circumference measurement will be obtained with anthropometric tape measure.
 - Thigh circumference will be measured at site of maximum bulge at Screening.
 Vertical distance of this site from the floor will be measured, such that thigh circumference measurements at all following study assessments are performed at the same site.
- 8. Caliper measurement of inner thigh skin-fold thickness will be obtained.
 - Caliper measurement will be performed at site of maximum bulge at Screening.
 Vertical distance of this site from the floor will be measured, such that caliper measurements at all following study assessments are performed at the same site.
- 9. Thigh gap measurement will be obtained.
 - Patient will be asked to stand with legs at a fixed distance apart. Measurement
 will be performed between sites of maximum bulge at Screening. Vertical

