Safety data will be collected at each visit of the study by study investigators and will be monitored by the Principal Investigator ([name]). Investigators will perform overall efficacy assessments of this study. The Principal Investigator will be reviewing data on an ongoing and consistent basis throughout the duration of the study. [name] will ensure that the study is conducted according to the protocol and that the data was accurately recorded. The Principal Investigator ([name]) is responsible for protecting the rights, safety, and welfare of subjects under his/her care. The Principal Investigator will be responsible for this review and for determining whether the research should be

altered or stopped. If any severe adverse effect or death directly related to the procedure proposed occurs, Principal Investigator will report to the IRB.

XI. Outcomes monitoring

Any adverse events will be reviewed and analyzed by the Principal Investigator as soon as the event occurs and will be documented in the subject's binder. Any unexpected adverse reactions will be reported by telephone to the IRB within 48 hours of observing the event. If a unexpected side effect occurs, Principal Investigator will also report adverse events to the FDA.

XII. Adverse event reporting guidelines

The principal investigator will follow the UCSD Human Research Committee guidelines for Adverse Event Reporting.

XIII. References

- Ingargiola M J, Motakef S, Chung M T, Vasconez H C, & Sasaki G H.
 Cryolipolysis for fat reduction and body contouring: safety and efficacy of current treatment paradigms. Plastic & Reconstructive Surgery. 2015;135(6):1581-1590.
- 3. Wollina U, & Goldman A. ATX-101 for reduction of submental fat. Expert opinion on pharmacotherapy. 2015;16(5):755-762.

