APPENDIX II. Post-Treatment Satisfaction Questionnaire

1. Were you satisfied with the Kybella treatments you received for reduction of inner thigh fat?

Yes/No

2. Have you noticed a reduction in inner thigh fat, compared to prior to treatments?

No improvement

0-25% improvement

25-50% improvement

50-75% improvement

75-100% improvement

3. Would you recommend Kybella treatments to a friend interested in reducing inner thigh fat?

Yes/No

4. Considering the side effects and disadvantages, would you undergo Kybella treatment for reduction of inner thigh fat again?

Yes/ No

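### Does an optional course of one to four sessions leave the primary component on adverse events leading to discontinuation uncountable?

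*Combined protocol and SAP*

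**What the plan says.** VI.A.1 and VI.B both list three primary safety incidences: any adverse event, serious adverse events, and "Adverse events leading to study drug discontinuation". The third is not defined further in either place. VI.B calls the study small and descriptive. Its safety population is subjects dosed at least once who have a later safety assessment, so at most the 15 enrolled (IV.A).

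The course is set in IV.D: "Subjects will receive 1 to 4 treatment sessions, each spaced 6 weeks +/- 1 week". On the later sessions it says: "Treatment #2, #3, or #4 will be pursued if patient desires more treatment, and if there is sufficient fat for treatment", the latter as the investigator judges. Tolerability is not named in that rule.

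Adverse events are asked for at the call two days after each session, at the second to fourth treatment visits, and at both follow-up visits (V.a). The follow-ups are tied to the last session actually given: "The visit will take place 4 weeks after the last treatment" and "The visit will take place 12 weeks after the last treatment". Section XI adds: "Any adverse events will be reviewed and analyzed by the Principal Investigator as soon as the event occurs". V.c refers to a Schedule of Events for the data to be collected, and X.A refers to case report forms and to notes to file in each subject's binder.

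**The concern.** With a fixed course, a subject who stops short stands out and someone asks why. Here any number of sessions from one to four is allowed, so a short course raises no flag. A subject who declines the second session because the first one hurt fits the description of a patient who does not want more treatment, and could be filed as having completed an allowed course.

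The visit and call lists in V.a do not close the gap. None has an item for why a session was not given. The questionnaire item, "Considering the side effects and disadvantages, would you undergo Kybella treatment for reduction of inner thigh fat again", takes yes or no and does not separate adverse events from other drawbacks. The rule in VI.B that on a subject's "early termination from study, missing values will be imputed" concerns leaving the study, not stopping injections while still attending follow-up.

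At stake is the meaning of a primary rate. A reported zero could mean that no adverse event stopped treatment, or that such stops were put down to preference. A reason not noted at the time is hard to recover later.

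**Working it through.** The plan gives no expected rate, precision or power for this component, so there is no stated figure to reproduce. The check covers what the wording counts, what is captured, and how much one subject matters.

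**1. What the wording counts.** The component asks whether an adverse event led to the drug being stopped. That is a question of cause, and it does not depend on a planned number of sessions. IV.D says when a further session is given; it does not say that a stop caused by an adverse event is a completed course. The ordinary reading therefore includes the subject who declines because of an adverse event.

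**2. Contacts at which adverse events are recorded.** For a subject with k sessions who attends everything, V.a gives k calls, k − 1 later treatment visits and 2 follow-ups:

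- contacts = k + (k − 1) + 2 = 2k + 1
- k = 1: 3 contacts; k = 4: 9 contacts

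**3. Timing against the decision to stop.**

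| Event | Days after last session |
|---|---|
| Week 4 follow-up | 4 × 7 = 28 |
| Next session would be due | 5 × 7 to 7 × 7 = 35 to 49 |
| Week 12 follow-up | 12 × 7 = 84 |

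For a subject who stops after session 1 these are Day 29, Day 36 to 50 and Day 85. Week 4 can come before the decision is final. Week 12 always comes after the window has closed, so every subject who stays in follow-up is seen by the investigator once the stop is a fact. The follow-up windows printed in V.a, Day 134 to 176 and Day 190 to 232, are the fourth-session window (Day 106 to 148) plus 28 and plus 84. They describe four-session subjects only, but the text tying each visit to the last treatment covers the rest.

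**4. Weight of one subject.** With all 15 in the safety population, one subject classified differently moves the rate by 1/15 = 6.7 points. Exact (Clopper-Pearson) 95% intervals, which the plan does not itself call for, are:

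| Count | Rate | 95% interval |
|---|---|---|
| 0/15 | 0% | 0 to 21.8% |
| 1/15 | 6.7% | 0.2 to 31.9% |
| 2/15 | 13.3% | 1.7 to 40.5% |

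The upper limit for 0/15 is 1 − 0.025^(1/15) = 21.8%. Neighbouring counts overlap almost entirely.

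**5. Illustration of missed stops.** Let p be the true rate of stops caused by adverse events and s the share recorded as such. The documents give neither, so both are assumed. The chance of reporting zero is (1 − p·s)^15:

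| p | s = 100% | s = 50% |
|---|---|---|
| 10% | 20.6% | 46.3% |
| 20% | 3.5% | 20.6% |
| 30% | 0.5% | 8.7% |

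The result depends wholly on s, about which the documents say nothing. The table shows that missed stops would matter if they happened; it is no evidence that they do.

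**6. Direction.** The missing definition is equally open the other way. VII.A describes injection-site reactions as common. An analyst who counted every short course that followed such a reaction would inflate the rate by the same 6.7 points per subject.

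**The case for a change.** The strongest case for a change is that this is a primary component, that the causal link is exactly what recording adverse events alone does not supply, and that the remedy is cheap: one sentence and one form field. The situation is also foreseeable. Section I.B reports moderate or severe pain in 60% of patients treated in the submental trials, though for a median of one day. Section IX pays $50 for each follow-up visit and nothing for treatment visits, so stopping injections while staying in follow-up is realistic. Notes to file are discretionary.

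What stands is that the term is not defined for an optional course and that no visit or call list in V.a names a reason for stopping. A written definition would be tidier.

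The rest does not carry the point. That the reason goes unrecorded cannot be shown: a field for it would normally sit in the Schedule of Events or the case report forms, and neither is in the text reviewed. The adverse event itself still counts in the first primary component. The cheap remedy also settles less than it seems to. A single main reason would let a subject with both pain and little benefit be coded as no benefit, and a subject lost before follow-up would have no reason recorded at all.

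**Conclusion.** No change to the plan is called for. The component is undefined for an optional course, but its ordinary meaning already covers a stop caused by an adverse event. Adverse events are sought at 3 to 9 contacts per subject, the last of them after the next session would have been due, and the principal investigator reviews each event as it occurs. At one centre with at most 15 subjects, the investigator can settle the few doubtful cases sensibly.

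The possible effect is 6.7 percentage points per subject, with the direction not established and the number of such subjects unknown. No test, threshold or decision rule depends on the rate, and the first two primary components are unaffected. The conclusion assumes that the component is read by cause, and that subjects who stop injections mostly stay to Week 12. It does not assume that a reason field exists, only that its absence cannot be inferred from the text available.
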